1 PROTOCOL SUMMARY

1.1 SYNOPSIS

- Title:** Data-informed Stepped Care (DiSC) to Improve Adolescent HIV Outcomes (UH3): A cluster randomized trial on a Data Informed Stepped Care intervention to improve retention among adolescents living with HIV
- Grant Number:** UH3 HD096906
- Study Description:** The goal of this study is to develop, pilot and test a Data informed Stepped Care (DiSC) Intervention in a cluster randomized controlled trial (cRCT). The intervention is comprised of a system to assign adolescents living with HIV (ALHIV) to different levels of care, depending on their current and anticipated health care needs.
- Objectives*:**
- Primary objective**
- Aim 1:** To develop, adapt, pilot, and optimize implementation of a data-informed stepped care (DiSC) intervention for ALHIV HIV treatment management.
- Aim 2:** To evaluate effectiveness of the DiSC intervention on ALHIV retention in up to 24 high-volume HIV clinics in Homabay, Kisumu and Migori counties in Western Kenya.
- Secondary objectives**
- Aim 1:** To determine acceptability, feasibility, adaptability and fidelity of the DiSC intervention
- Aim 2:** To evaluate the effectiveness of the DiSC intervention on ALHIV cascade outcomes (adherence, viral suppression) and adolescent self-efficacy, health service outcomes, implementation outcomes in high volume HIV clinics in Homabay, Kisumu and Migori counties.

Endpoints*:	Primary Endpoint: % retained at 6 and 12 months Secondary Endpoints: % virally suppressed at 6 and 12 months after ART initiation, proportion with >80% adherence since last refill, % retained at 18 and 24 months, adolescent self-efficacy and correlates of retention and viral suppression. Secondary implementation outcomes: intervention reach, adoption, fidelity, acceptability, feasibility, implementation and maintenance.
Study Population:	Up to 40 Health care workers (HCW), youth, policy makers and stakeholders in adolescent HIV care (aim 1 intervention development), HCW in 2 clinics in Kenya (aim 1 pilot) 6000medical records of adolescents and young adults ages 10-24 years enrolled in HIV care, and HCW in participating facilities, Approximately 3000 HIV positive adolescents and young adults,900 caregivers of HIV positive adolescents and young adults and a 200 HCWs. (Aim 2).
Phase* or Stage:	Phase III Clinical Trial
Description of Sites/Facilities Enrolling Participants:	Aim 1: 2 HIV clinics in Homa-bay, Migori or Kisumu. Aim 2: up to 24 HIV clinics in Homa-bay, Migori or Kisumu.
Description of Study Intervention/Experimental Manipulation:	Data-informed Stepped Care (DiSC) intervention is comprised of a system to assign ALHIV to different levels of care depending on their current and anticipated health care needs. The intervention will be delivered at the individual level by HCW providing routine care during routine HIV clinic visits.
Study Duration*:	24 months
Participant Duration:	24 months

1.2 SCHEMA

1.3 SCHEDULE OF ACTIVITIES

	Outcome assessed	Pre-screening (Pre-consent)	Enrollment	Enrollment Month 0±2	Month 6 Month 6±2	Month 12 Month 12±2	Unscheduled Visits
Clinic Eligibility		X					
Aim 2							
EMR data abstractions	Retention, viral non suppression		X	X	X	X	
Informed Consent (surveys)	NA		X				
Caregiver/adolescent surveys	Secondary outcomes		X		X	X	
HCW surveys	Health service & Implementation outcomes		X			X	
HCW implementation logs/surveys	Implementation outcomes						X
HCW implementation surveys, IDI /FGD (intervention sites only)	Implementation outcomes				X		
Facility surveys	Implementation outcomes		X			X	
Adolescent/caregiver satisfaction surveys (intervention only)	Implementation outcomes					X	
Adolescent FGDs	Implementation outcomes						
Randomization	NA	X					

2 INTRODUCTION

2.1 STUDY RATIONALE

UNAIDS '95-95-95' targets cannot be achieved without additional support for adolescents living with HIV (ALHIV) to increase retention in care and to support viral suppression. Risk prediction tools as well as a stepped care approach to care can support differentiation of ALHIV to different risk groups, and tailor care based on risk.

Our team has conducted formative work with ALHIV, caregivers, HCW and policy makers and has developed and validated a clinical prediction tool to identify ALHIV at highest risk of not being retained in care and poor viral suppression that could be adapted to identify adolescents who may need more support in their care. Understanding how best to use the risk prediction tool as well as how to tailor services based on risk may ultimately result in more efficient HIV care services, as well as adequate support for ALHIV at highest risk of poor outcomes.

This study aims to test a data informed stepped care approach to improve retention and viral suppression among ALHIV. We will also study implementation and service delivery outcomes.

2.2 BACKGROUND

B1. Adolescents are disproportionately affected by HIV

Adolescents represent an estimated 40% of new infections worldwide,[2] and 84% of HIV-infected adolescents live in sub-Saharan Africa (sSA).[3] In Kenya, HIV incidence among adolescents has increased by 17% since 2013, while incidence has reduced by 19% in adults and 49% in children.[4]The majority (91%) of AIDS-related deaths among adolescents in the region have not declined (Figure 1).[5] A growing number of perinatally infected adolescents will need lifelong antiretroviral therapy (ART).[6, 7]**'90-90-90' targets cannot be achieved without substantially increasing engagement in care and viral suppression among adolescents.**

[figure not shown]

Figure 1: Static mortality among 10-19 year

B2. Adolescent HIV care cascade outcomes are poor

Adolescents in African countries have lower retention, adherence to ART [8] and viral suppression compared to adults.[8-14] Loss to follow-up (LTFU) among adolescents within the first 12 months of treatment ranges from 15% to 83%.[12, 15, 16] Poor ART adherence is common and increases risk of HIV transmission and disease progression.[17, 18] The greatest gap in the adolescent care cascade is viral load, [19, 20] with >30% experiencing virologic non-suppression or failure after 12 months on ART.[7, 21-24]Lack of viral suppression among adolescents undermines progress in retention and adherence.

Adapted from NIH Behavioral and Social Intervention Clinical Trial Protocol Template v3.0 - 20180827

B3. Reasons for poor adolescent engagement in care are unclear and varied

Cofactors of viral suppression may be distinct in this age group. Male gender, poor mental health,[25] stigma, substance use,[25] fear of provider judgement, [26] lack of support,[27, 28] and school barriers [29] are risk factors for poor adherence and retention among adolescents, though data are limited.[30] Lack of age-disaggregated data in research and programs in high-burden settings remains a major barrier to responding effectively to the adolescent HIV epidemic.[31, 32]**Systematic cohort data on social, behavior, and clinical factors affecting retention and treatment outcomes are necessary to inform new HIV care interventions for adolescents.**

B4. Adolescence is a unique period of life, with specific challenges for HIV-infected adolescents

Adolescence is a time of rapid physical, cognitive, sexual, and social transition, characterized by increased autonomy, experimentation, growing peer influence, and identity formation.[33] These contexts and behaviors affect health outcomes in adulthood and next generations.[34, 35] Adolescents with HIV face unique challenges transitioning successfully to adulthood and achieving optimal health.[11, 36] Younger adolescents (10-14) are more likely to be perinatally infected, live at home, and have parental supervision. Many do not know their status or have been recently disclosed to.[37, 38] Older adolescents want more autonomy to make choices about relationships and health, but have decision-making challenges.[34, 39, 40] Adolescent females have added risk of poor adherence due to relationship violence[41] while gender norms and lack of targeted services are linked to lower male engagement in care.[42] **New interventions to optimize retention and clinical outcomes must be tailored to adolescents' developmental, health, and social needs.**

B5. Caregivers influence clinical outcomes in adolescents, but need support

Parents or non-parent caregivers are the primary sources of support, social norms, and supervision in early adolescence.[43] Caregivers have the potential to improve adolescent disclosure, treatment adherence, and retention, but feel ill-prepared for this role.[37, 38, 44] A trial conducted in Zimbabwe found that a community health worker-led intervention to train and support caregivers resulted in a significant reduction in viral non-suppression or mortality in their HIV-infected children.[45]**Caregiver perspectives are necessary to inform adolescent services and to improve clinical outcomes in adolescents.**

B6. 'Test and Start' will burden health systems in resource-constrained settings

Adoption of Test and Start models, where all persons living with HIV are rapidly initiated on treatment, addresses loss to follow-up in the pre-ART period as part of initiatives to reach 90-90-90 goals, with early evidence of success.[46] However, there are fears that increasing caseloads and HCW burden in already strained healthcare systems will result in difficulty accessing or poor quality of care.[47] Differentiated models of service delivery have been proposed as a client-centered approach that simplifies and adapts HIV services across the cascade to better serve those in care and to reduce unnecessary burdens on the health system.[48] Due to poor retention outcomes, Kenyan guidelines currently classify all adolescents as "unstable",[49] thus not able to access differentiated approaches, like community models or longer refill durations, which may benefit for this population.

Adapted from NIH Behavioral and Social Intervention Clinical Trial Protocol Template v3.0 - 20180827

B7. “Stepped care” as an evidence-based model for differentiated care

The stepped care model grounded in Stages of Change Theory,[50]has been used in mental health fields to organize provision of services; and to support clients, HCW, and caregivers to identify the most effective interventions (Figure 2).[51] Models typically start with a low-intensity, evidence-based treatment, and systematically progress to higher levels of care or intervention as clients fail to respond.[52] **A key feature of stepped care is outcome monitoring, giving both clients and HCWs feedback to inform care options and service delivery.** Early studies suggest improvements in access to care, client outcomes, and program efficiencies, including client volume.[53] A systematic

review found effectiveness on 6-month depression outcomes,[54] and a randomized trial demonstrated reduced incidence of depression and anxiety among older adults.[55]

B8. Clinical prediction tools identify high-risk individuals for interventional support

Clinical prediction tools are useful to classify individuals into high and low risk groups, to identify those in need of intervention, and to deliver services more efficiently.[56-59] Studies among MSM in the United States [56, 59] and two studies in Kenya found that clinical characteristics were predictive of HIV risk.[58, 60]Tools validated in clinic cohorts of HIV-infected adults in the US [61] and in low resource settings [62] have shown to be predictive of virologic failure or mortality using minimal variables.[61-63]**Prediction tools could enable HCWs to provide better support to adolescents at risk for poor outcomes rather than waiting until poor outcomes occur.**

B9. Health systems interventions may improve adolescents care cascade and clinical outcomes

Despite nearly 15 years of research to improve retention outcomes in adults, there is lack of evidence of what works for HIV-infected adolescents.[64-66] Individual psychosocial interventions may improve ART adherence for adolescents at risk of treatment failure, [65] but alone are not sustainable in high-burden countries. Health systems interventions can empower HCWs to tailor services for their unique population needs and optimize limited resources.[48] A US study found that multidisciplinary care teams improve adolescent retention in care, [67] and the SAIA trial used a systems engineering approach to triple ART coverage for prevention of mother to child transmission in Africa.[68] **It is plausible that a health systems approach, using a data-driven, provider-led intervention to optimize adolescent HIV services, may result in health services efficiencies and improved adolescent HIV care engagement and clinical outcomes.**

C. INNOVATION

Adapted from NIH Behavioral and Social Intervention Clinical Trial Protocol Template v3.0 - 20180827

- A clinical prediction tool can identify adolescents at risk for loss to care before negative clinical outcomes occur. Simple, practical tools can be incorporated into routine data collection to identify adolescents at highest risk of disengagement **before** loss to care, providing an opportunity for health systems to intervene.
- Stepped care models paired with accurate risk identification can reach priority adolescents without increasing burden on the health system. There are great concerns about the capacity of health systems to manage care in the ‘Test and Start’ era. Stepped care models use programmatic data to target services to those most in need. This framework is highly aligned with international movements for differentiated care.
- Current Kenyan guidelines for differentiated care do not include adolescents. All HIV-infected adolescents are considered “unstable” and thus not eligible for differentiated HIV services under current Kenyan guidelines.[49] This approach masks heterogeneity and diverse needs. Carefully and systematically assessing individual risk can identify those who need heightened services, as well as those at lower risk, who may benefit from less intensive or frequent clinic visits according to differentiated care models.
- A health systems intervention can be widely applied across different settings. Despite national roll out of the Adolescent Package of Care (APoC) guidelines, large scale and local programs targeting adolescents with HIV are not uniform. A health systems approach can be applied across clinical facilities to enhance diverse interventions by matching them to client characteristics and specific health system compositions.
- Client-centered interventions that involve providers, families, and youth in design and implementation can maximize uptake and impact. Youth perspectives are critical to engagement in HIV research and programs and to determine what additional support might be needed.[69] Addressing legal and ethical considerations can maximize representative participation and better inform design and delivery.
- Effectiveness research is necessary to develop sustainable models for adolescent HIV care: We will evaluate the DiSC intervention by leveraging routine electronic medical record (EMR) data and clinic populations and engaging community stakeholders throughout the study lifecycle. By approximating real-world conditions, we maximize generalizability and sustainability of this model in resource-limited settings.[70]
- Using an implementation-effectiveness hybrid design improves translation to practice: Our study is structured *a priori* to address both clinical intervention and implementation outcomes. Use of hybrid study designs may improve policy relevance and public health impact of new interventions.[71]

IMPACT: A data-driven, provider-led, health systems intervention can identify adolescents most at risk for loss to care, sub-optimal adherence, and viral failure. Our stepped care approach, combined with a clinical prediction tool, is a timely and flexible intervention in the context of differentiated care and numerous ongoing care initiatives. By improving adolescent engagement in care and optimizing provision of limited resources, this intervention can ultimately improve health and decrease HIV transmission risk among adolescents in Kenya.

2.3 RISK/BENEFIT ASSESSMENT

2.3.1 KNOWNPOTENTIAL RISKS

Adapted from NIH Behavioral and Social Intervention Clinical Trial Protocol Template v3.0 - 20180827

There are no medical interventions associated with the study, therefore we anticipate no risk of serious physical harm to participating HCWs, adolescents or caregivers. In all HIV research studies there is a non-negligible risk of loss of confidentiality of HIV status or other medical information. There is also risk of emotional discomfort when responding to sensitive personal questions. HCWs who are trained in the DiSC intervention may have concerns about job loss if they perform poorly in implementing the stepped care approach. There is a possibility for social harm (depression, violence after disclosure, abandonment) related to routine HIV treatment and management during clinical encounters with routine providers during the course of the study. However, the possibility of this social harm would exist if this intervention were not conducted. There is a possibility that during a clinical encounter with the more intensive care steps, an ALHIV may be more comfortable disclosing that they are suffering from previously undiagnosed mental health problems such as depression. Any patients with potential mental health problems will be referred for psychosocial support at the facility or nearest referral hospital, according to standard HIV care and treatment guidelines for adolescents at that clinic.

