2.3.3 ASSESSMENT OF POTENTIAL RISKS AND BENEFITS

All adult study participants will have the study and relevant study procedures explained to them, their questions answered, and provide written consent for their enrollment.

Together, the UW, Nairobi, and Kisumu Study Team has more than 10 years' experience managing HIV-infected children and adolescents and in clinical trials and observational research and will take every precaution to protect participants' and their caregivers' confidentiality. All study staff will have been trained in the Protection of Human Subjects and new staff will receive similar training.

Procedures to minimize physical risks: There are no medical interventions associated with the study, therefore we anticipate no risk of serious harm to study participants.

Procedures to minimize confidentiality risks: All key personnel will be trained in the Protection of Human Subjects. The field team will take every precaution to protect participants' confidentiality. We will only collect personal identifiers for the purposes of identifying and contacting participants about the study. This information will include the names, telephone numbers and emails for those identified as interested in participating in the study. Personal identifiers will be used to contact stakeholders in aim 1 and HCWs to remind them of their scheduled study activities. This information will also be used to contact them again to verify the accuracy of the information

Adapted from NIH Behavioral and Social Intervention Clinical Trial Protocol Template v3.0 - 20180827

collected or to elaborate or clarify certain information provided during study procedures if they select the option to be re-contacted on the consent form.

All participants will be assigned a study identification number (ID). Participant identifiers will be linked to their study ID in a link-log document that will be stored separately from all other study data. Only necessary study staff will have access to this document and will not share this information with other study staff or with others outside of this study.

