behavioral surveys at enrollment and every 6 months thereafter. Clinic staff members will refer to the study team a purposeful sample of caregivers of adolescents coming in for routine clinic visits. A large number of adolescents come to clinic alone; the study will only recruit caregivers who accompany adolescents. Caregivers who meet eligibility criteria will be invited to enroll and complete caregiver surveys at enrollment and at 12 months.

HCW surveys

HCW in participating sites working in the ALHIV clinic will be invited to participate in health service and implementation surveys. A script outlining talking points, purpose and scope of work will be used for recruitment. Written informed consent for participation will be collected from all participants prior to study activities.

Participant incentives

The study will provide reimbursement for transportation costs, accommodation and meals during the workshop and provide a per-diem allowance equal to current rates used by organizations or facilities where the HCWs work.

Adolescents and caregivers who participate in surveys will be reimbursed KSH 200 (\$2.00 USD). HCW attending study related meetings and completing surveys will be reimbursed KSH 1000 (~10USD).

Population justification

This study will be conducted in ALHIV age 10-24 years old, who have a high risk of mortality, and require innovative client-centered strategies to improve retention, adherence, and viral suppression. The study will be conducted in Kenya, where 140,000 adolescents (ages 10-19) have HIV, and HIV is among the leading causes of mortality in this age group.

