6 STUDY INTERVENTION(S) OR EXPERIMENTAL MANIPULATION(S)

6.1 STUDY INTERVENTION(S) OR EXPERIMENTAL MANIPULATION(S) ADMINISTRATION

6.1.1 STUDY INTERVENTION OR EXPERIMENTAL MANIPULATION DESCRIPTION

The Data-informed Stepped Care (DiSC) intervention is comprised of a system to assign ALHIV to different levels of care, or “steps”, depending on their current and anticipated health care needs. Stepped care is a model grounded in Stages of Change Theory and has been used in mental health fields to organize provision of services, and to support clients, HCWs, and caregivers to identify interventions tailored to individual need. HCWs at participating sites will assign ALHIV to different levels or intensity of HIV services. The trajectory of services moves from a relative position of ALHIV autonomy to more intensive service provision. Intervention steps could start with multi-month refills or community treatment delivery, then social support activities (support groups, life skills activities), progress to individualized services (text messaging, ‘big brother/sister’ older peer support, motivational interviewing), and ultimately a case management approach involving referrals to specialized care like mental health or gender-based violence services, individualized counseling, and active tracking of individual participation in support and care services. The stepped care framework is designed to be flexible, to accommodate variable

Adapted from NIH Behavioral and Social Intervention Clinical Trial Protocol Template v3.0 - 20180827

individual and social support services available at each facility. A sample of potential intervention steps is presented below:

Sample intervention steps

Levels	Criteria for eligibility	Regular care	Additional HCW provided	Additional clinic recommended
Stepped down care	Meets MoH criteria except age	-Differentiated care	None	-Support groups (optional)
Not retained	At risk for loss	-3 monthly visits	-Pre-clinic reminders (text) -Individual peer support -3 monthly adherence counseling	-Support group
Viral failure	At risk for viral failure OR VL under 1000 but detectable	-Monthly visits (6 weekly for school going)	-Monthly adherence counseling -Motivational interviewing (one round of several sessions) OR Coaching -Individualized ART pick-up strategies	-Support group -Caregiver or support person DOTS

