Failed	Unsuppressed at last measure	-Monthly visits (6 weekly for school going)	-2 weekly adherence sessions (could make some on phone) -Accelerated repeat test timeline (3 month) -Prompt switch after second test -Case manager -DOTS by HCW (or caregiver/family)	-Support group -Special treatment failure support groups -Home visit by HCW -Viremia clinics

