8.2 SAFETY ASSESSMENTS

We do not anticipate adverse events associated with the intervention, and therefore we will not actively monitor for adverse events. However, if any adverse events occur among participants enrolled in the study, we will report them as required by the regulatory bodies.

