9.4.2 ANALYSIS OF THE PRIMARY ENDPOINT(S)

Adapted from NIH Behavioral and Social Intervention Clinical Trial Protocol Template v3.0 - 20180827

Mixed effects regression models will be used to compare the number of missed visits between arms, accounting for clustering by individual and clinic. LTFU will be compared using cox proportional hazards regression. Death or transfers will be censored. Sub-group analyses will be performed by gender and age-group. Facility factors, including concurrent adolescent-friendly services and high/low performance will be evaluated as moderators of intervention effectiveness.

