9.4.4 SAFETY ANALYSES

NA

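### The protocol says there is no medical intervention and plans no safety analysis, although its sample steps touch ART switching and visit frequency; deaths recorded in the EMR are only censored, and no outcome, model or summary table compares them by arm

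*Protocol*

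**What the plan says.** **Premise.** Protocol 2.3.1 says: "There are no medical interventions associated with the study, therefore we anticipate no risk of serious physical harm to participating HCWs, adolescents or caregivers". Section 2.3.3 repeats it: "There are no medical interventions associated with the study, therefore we anticipate no risk of serious harm to study participants".

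**Monitoring and analysis.** Protocol 8.2: "We do not anticipate adverse events associated with the intervention, and therefore we will not actively monitor for adverse events". Section 8.3.4, on the period and frequency of event assessment, is marked NA. So is section 9.4.4, headed "SAFETY ANALYSES".

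**Sample steps.** In the table in protocol 6.1.1, the step for unsuppressed viral load includes a faster repeat test and "Prompt switch after second test". The stepped-down group is defined by "Meets MoH criteria except age", and visit frequency is set by step. SAP 3.5.3 makes receipt of differentiated care, including visits scheduled three months or more ahead, a secondary outcome.

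**Deaths.** Protocol 5.5 describes a population "who have a high risk of mortality". Section 9.4.2 says: "Death or transfers will be censored". SAP Table 1 and section 3.5.1 do the same for loss to follow-up, and SAP Table 4 excludes appointments whose status is censored.

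**DSMB.** Protocol 10.1.6 has the board assess safety data from each arm every year. SAP Section 5 has adverse events monitored as they come up, reviewed unblinded, with recommendations on imbalances. Its SAE listing has a study-arm column.

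**The concern.** The statement that nothing medical is being changed does not fit the only intervention steps that the documents show. Sections 8.2 and 9.4.4, which plan neither active monitoring nor a safety analysis, also do not fit protocol 10.1.6 and SAP Section 5, which expect a board to judge safety by arm.

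Death is where this matters most. A person marked as died leaves the loss-to-follow-up analysis at that date, and later appointments with censored status leave the missed-visit model. If recorded deaths differed between arms, the planned effect estimates are not built to show it. The DSMB could see reported cases, but the documents do not say that it would see the deaths held in the EMR, or the person-time needed to judge them.

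**Working it through.** There is no figure in the plan to reproduce, so the main check is a comparison of texts. The arithmetic only shows what a death comparison could tell.

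**1. Premise against steps.** Protocol 2.3.1 and 2.3.3 say there is no medical intervention. The 6.1.1 table lists an ART switch, an accelerated viral load test and step-specific visit intervals. Protocol 2.2 says national guidelines class all adolescents as unstable and so not eligible for differentiated services, whereas the stepped-down group is selected on every ministry criterion but age. The table is labelled a sample. SAP 3.5.3 nevertheless measures a change in visit spacing whatever the final steps are.

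**2. Where a death can appear.**
- Outcome tables (protocol 8.1, SAP Table 1): death is not an outcome.
- Missed-visit model (SAP 3.4, Table 4): appointments with censored status are excluded.
- Loss to follow-up (SAP 3.5.1, Table 5): deaths are censored with transfers, and there is no row for deaths.
- SAE listing (SAP Section 5): one line per reported event, with arm, but no denominator, person-time or rate.
- CONSORT figure: not shown in the text available, so it may carry a count.

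**3. What feeds the listing.** Protocol 8.2 covers events among enrolled participants and rules out active monitoring. Table 3b plans 3,000 EMR records per arm. No passage sends deaths in those records to the listing. Reporting could also differ by arm: the trial is unblinded, intervention sites hold twice-monthly meetings in the first six months (protocol 8.1), and Table 3b plans 12 implementation logs for intervention and 0 for control, although protocol 8.1 mentions some control-site data. EMR abstraction covers both arms alike.

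**4. Precision of a death comparison.** Inputs: 3,000 per arm (Table 3b) and 12 clinics per arm (SAP 2.2.1), so 3,000/12 = 250 per clinic. Assumptions, because the documents give neither: 12-month mortality of 0.5% or 1% in one arm, doubled in the other, and an ICC for death of 0 or 0.005.

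Design effect = 1 + (250 − 1) × 0.005 = 2.245.

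95% CI = exp(ln 2 ± 1.96 × √[DE × (1/a + 1/b)]), with a and b the deaths per arm.

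| Deaths | ICC 0 | ICC 0.005 |
|---|---|---|
| 15 vs 30 | 1.08 to 3.72 | 0.79 to 5.06 |
| 30 vs 60 | 1.29 to 3.10 | 1.04 to 3.86 |

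With the ICC of 0.005 the effective size is 3,000/2.245 ≈ 1,336 per arm. Two-sided power at 0.05 to detect the doubling (normal approximation for two proportions) is then about 32% and 57%.

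SAP 2.2.1 expects 100 to 200 AYA per clinic, which over 12 clinics is 1,200 to 2,400 per arm. At 0.5% versus 1% that gives 6 vs 12 deaths (0.75 to 5.33) or 12 vs 24 (1.00 to 4.00), even without clustering.

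**The case against.** A reader might infer that an excess of deaths in one arm would appear in no planned comparison at all. The documents do not support that. Protocol 10.1.6 and SAP Section 5 plan a DSMB review by arm, including imbalances. Grade 3 to 5 events count as serious (protocol 8.3.2), so a reported death falls under that review. The DSMB charter, which is to define what the board sees, is not among the documents, so it cannot be said that the board will lack a count; only that the protocol and SAP provide none.

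Nor would such an arm necessarily look no worse on every outcome. Only people marked as died are censored. A death not recorded in the EMR would show as missed visits or loss to follow-up. Viral non-suppression and adherence, where harm from changed care might first show, are compared by arm. The missed-visit and loss ratios would stay unmoved only if every excess death were recorded and survivors behaved the same.

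Other points also stand. The steps are illustrative, to be settled by the workshop and pilot, and some of their visit intervals lie within the usual 1 to 3 months in control (protocol 4.1). Section 8.2 gives its own reason (no adverse events anticipated) and 9.4.4 gives none, so neither can be shown to follow from 2.3.1. Protocol section 9 describes itself as a summary of the SAP, so its NA is not the last word. Regimen is not among the EMR fields named in protocol 8.1.

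The gap remains after all this: the board's route is passive, has no denominator, and is not tied to the deaths that the SAP itself uses for censoring.

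**Conclusion.** The point holds in limited form. The no-medical-intervention statement conflicts with the sample steps. Protocol 8.2 and 9.4.4 conflict with protocol 10.1.6 and SAP Section 5. Recorded deaths enter the plan only as a censoring event, with no outcome, model or summary table comparing them by arm.

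The size of any missed difference cannot be stated, because the documents give neither mortality nor an ICC for death. Under the assumptions above, even a doubling would often be compatible with no difference once clustering is allowed for. A death table is therefore descriptive and not a powered test, and it would be wrong to claim that a doubling would reliably be visible in it. This is a cheap improvement to safety reporting and not a flaw in the primary analysis.

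**What to change.** 1. Reconcile protocol 2.3.1, 2.3.3, 8.2 and 9.4.4 with the steps in 6.1.1, with protocol 10.1.6 and with SAP Section 5. Which clinical steps are right is for the investigators.
2. In place of NA in 9.4.4, and in SAP Section 5, plan a descriptive table of EMR-recorded all-cause deaths by arm: counts, person-years, rate, and a rate ratio with a confidence interval that allows for clinic clustering.
3. Send that table to the DSMB at each annual meeting and report it with the final results.
4. Tabulate ART regimen changes by arm only if the abstracted data hold them, and read them as delivery of the intervention and not as harm, since a sample step itself prompts switching.

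The cost is some protocol wording and one SAP table. The died marker is already needed in both arms for censoring, so there is no new procedure. The drawbacks are few events and wide intervals, and deaths that never reach the EMR stay uncounted.
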